12.5 Archiving and data retention

The Investigator will maintain adequate records for the study, including eCRFs, medical records, laboratory results, Informed Consent documents, drug dispensing and disposition records, safety reports, information regarding subjects who discontinued, and other pertinent data.

All essential documents are to be retained by the Investigator until at least 2 years after the last approval of a marketing application in an ICH region and until there are no pending or contemplated marketing applications in an ICH region, or at least 2 years have elapsed since the formal discontinuation of clinical development of the IMP. These documents should be retained for a longer period; however, if required by the applicable regulatory requirement(s) or by an agreement with UCB (CPMP/ICH/135/95, 2002 [Section 4.9.5]). The Investigator will contact UCB for authorization prior to the destruction of any study records or in the event of accidental

loss or destruction of any study records. The Investigator will also notify UCB should he/she relocate or move the study-related files to a location other than that specified in the Sponsor's Study Master File.

12.6 Audit and inspection

The Investigator will permit study-related audits mandated by UCB, after reasonable notice, and inspections by domestic or foreign regulatory authorities.

The main purposes of an audit or inspection are to confirm that the rights and well-being of the subjects enrolled have been protected, that enrolled subjects (ie, signing consent and undergoing study procedures) are appropriate for the study, and that all data relevant for the evaluation of the IMP have been processed and reported in compliance with the planned arrangements, the protocol, investigational site, and IRB/IEC SOPs, ICH-GCP, and applicable regulatory requirements.

The Investigator will provide direct access to all study documents, source records, and source data. If an inspection by a regulatory authority is announced, the Investigator will immediately inform UCB (or designee).

12.7 Good Clinical Practice

Noncompliance with the protocol, ICH-GCP, or local regulatory requirements by the Investigator, institution, institution staff, or designees of the Sponsor will lead to prompt action by UCB to secure compliance. Continued noncompliance may result in the termination of the site's involvement in the study.

13 STATISTICS

A description of the planned statistical methods is provided in the sections that follow. Full details will be provided in the Statistical Analysis Plan (SAP).

13.1 Definition of analysis sets

13.1.1 Enrolled Set

The Enrolled Set consists of all subjects who have given informed consent.

13.1.2 Randomized Set

The Randomized Set (RS) consists of all subjects randomized into the study.

13.1.3 Safety Set

The Safety Set (SS) consists of all subjects who were administered at least 1 dose or a partial dose of IMP. The SS will be used to summarize and analyze all safety variables. In case of dosing administration error, summaries and analyses using the SS will be conducted according to actual treatment received.

13.1.4 Full Analysis Set

The Full Analysis Set (FAS) consists of all subjects in the RS who were administered at least 1 dose or a partial dose of IMP and have Baseline and at least 1 post-Baseline seizure frequency data during the Treatment Period. In case of dosing administration error, or change in treatment

dose, summaries and analyses using the FAS will be conducted according to randomized treatment. The FAS will be the primary analysis set for all efficacy summaries and analyses.

13.1.5 Per-Protocol Set

The Per-Protocol Set (PPS) is a subset of the FAS, consisting of those subjects who had at least 1 post-Baseline efficacy measurement and who had no major protocol deviation affecting the primary efficacy variable, as confirmed during a pre-analysis data review meeting, conducted prior to study unblinding.

13.1.6 Pharmacokinetic/Pharmacodynamic Set

The Pharmacokinetic/Pharmacodynamic Set is defined as a subset of the FAS, consisting of those subjects who provide at least 1 PSL concentration measure and at least 1 post-Baseline PD variable.

13.2 General statistical considerations

Summary statistics will be provided for all efficacy, safety, and Baseline demographic variables. Summary statistics will consist of frequency tables for categorical variables. For continuous variables, descriptive statistics (number of available observations, mean, median, standard deviation [SD], standard error, minimum, maximum, 25th and 75th percentiles) will be tabulated. Unless otherwise mentioned, statistical hypothesis tests will be 2-sided at the 5% significance level.

13.3 Planned efficacy analyses

The efficacy variables will be analyzed as described below using the FAS.

Total seizure frequency per 28 days will be derived from the seizure count information recorded on the diary card and is defined as the number of seizures standardized to a 28-day period. It is computed as the number of seizures recorded over a period, divided by the total number of days in that period, multiplied by 28. Observable focal-onset seizures refers to Type IA1, IB, and IC seizures (according to the ILAE Classification of Epileptic Seizures, 1981). Focal-onset seizures include all Type I seizures. Seizure free status and seizure-free days include all (Type I, II, and III) seizure types.

13.3.1 Analysis of the primary efficacy variable

13.3.1.1 Analysis of the primary efficacy variable for the US FDA, PMDA, and other regulatory authorities not specified in Section 4.1.1.2

Pairwise comparisons of 400mg, 200mg and 100mg dose groups versus placebo will be carried out using the analysis model below. Type 1 error will be controlled by the Hochberg step-up procedure within SAS® Proc Multtest. If all the results of the pairwise comparisons are statistically significant then the 50mg dose group will be compared to placebo.

For the US FDA, PMDA, and other regulatory authorities not specified in Section 4.1.1.2, the primary efficacy variable is the change in log-transformed observable focal-onset seizure frequency from Baseline, over the 12-week Maintenance Period. The 28-day Baseline and post-Baseline (maintenance) seizure frequency will be transformed with the natural logarithm, specifically $\ln(x+1)$, where x represents the 28-day seizure frequency. The transformed seizure frequency data will be analyzed using analysis of covariance (ANCOVA) with treatment group

as the main factor, Baseline log-adjusted seizure frequency as a continuous covariate, and Baseline SV2A use and Region as categorical factors. Pairwise contrasts will be constructed to compute estimated effects of each dose from placebo.

All pairwise analyses of the primary efficacy variable will be repeated on the PPS.

13.3.1.2 Analysis of the primary efficacy variable for EMA and regulatory authorities who reference EMA

For EMA and regulatory authorities who reference EMA, the primary efficacy variable will be the 75% responder rate in observable focal-onset seizures during the Maintenance Period and will be analyzed using logistic regression with factors for treatment group, Baseline seizure frequency, Region, and Baseline SV2A use. If there are issues with convergence, Baseline SV2A use will be dropped.

The same methodology carried out in Section 13.3.1.1 will be applied to the pairwise analyses.

13.3.2 Secondary efficacy analysis

13.3.2.1 Secondary efficacy variables for the US FDA, PMDA, and other regulatory authorities not specified in Section 4.1.1.2

The 75% responder rate in observable focal-onset seizures during the Maintenance Period is a secondary efficacy variable for the FDA. It is the primary efficacy variable for EMA. The analyses are described in Section 13.3.1.2.

In addition, the 50% responder rate in observable focal-onset seizures during the Maintenance Period will be analyzed using logistic regression as described in Section 13.3.1.2. Analyses of the percent change in seizure reduction endpoints will be performed using the Wilcoxon-Mann-Whitney test. The Hodges-Lehmann nonparametric estimator will be used to estimate the median percent reduction in seizures between groups and its corresponding 95% confidence interval (CI) will be provided.

13.3.2.2 Secondary efficacy variables for EMA and regulatory authorities who reference EMA

The change in log-transformed observable focal-onset seizure frequency from Baseline, over the 12-week Maintenance Period is a secondary efficacy variable for EMA. It is the primary efficacy variable for the FDA. The analyses are described in Section 13.3.1.1.

In addition, the 50% responder rate in observable focal-onset seizures during the Maintenance Period will be analyzed using logistic regression as described in Section 13.3.1.2.

Analyses of the percent change in seizure reduction endpoints will be performed using the Wilcoxon-Mann-Whitney test. The Hodges-Lehmann nonparametric estimator will be used to estimate the median percent reduction in seizures between groups and its corresponding 95% CI will be provided.

13.3.3 Other efficacy analyses

All other analyses of the 75% and 50% responder rate endpoints will be analyzed using the same logistic regression model as specified in Section 13.3.1.2. Analyses of 90% responder rate and seizure freedom will use the same methodology. In addition to observable focal-onset seizures

and focal-onset seizures, analyses will also be carried out on all seizures (seizure-free status and seizure-free days) during the 12-week Maintenance Period and the 16-week Treatment Period.

All other analyses of the change from Baseline in seizure frequency will be analyzed using the ANCOVA model on the log-transformed data, as specified in Section 13.3.1.1.

The time to return to baseline 28-day observable focal-onset seizure count during the 12-week Maintenance Period will be analyzed using Kaplan-Meier methodology. Additional details of the analysis will be captured in the SAP.

The QOLIE-31-P and SSG assessments will be summarized using descriptive statistics by each available visit.

13.4 Planned safety and other analyses

13.4.1 Safety analyses

Adverse events will be coded using the Medical Dictionary for Regulatory Activities (MedDRA[®]). Adverse events will be summarized by MedDRA system organ class and preferred term. The incidence of SAEs, AEs leading to premature discontinuation or dose tapering, and related AEs, and the incidence of AEs by maximum intensity, will also be summarized.

Laboratory values, ECG data (ventricular rate, PR, QTcB, QTcF, and QRS) and arrhythmias, vital signs, weight, and changes from Baseline in these measures will be summarized by period, visit, and treatment group. Possibly clinically significant treatment emergent abnormalities for laboratory values, vital signs, and weight will be listed and summarized by period and visit for each treatment group.

Electrocardiogram abnormalities as well as physical and neurological abnormalities will also be listed by period and visit. Quantitative safety parameters will be summarized descriptively by time point and treatment group. Categorical safety summaries will provide the number and percentage of subjects within each summarized category.

Doppler echocardiogram results at Baseline and during and after treatment, and changes from Baseline, will be listed and descriptively summarized.

All C-SSRS data obtained at Baseline and subsequent visits will be reported as a listing ordered by subject and visit. Psychiatric and Mental Status assessment and CIWA-B data will also be included using listings.

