6.3 Withdrawal criteria

Subjects are free to withdraw from the study at any time, without prejudice to their continued care.

Subjects should be withdrawn from the study if any of the following events occur:

1. Subject withdraws his/her consent.
2. The Sponsor or a regulatory agency requests withdrawal of the subject.
3. Subject is noncompliant with the study procedures or medications in the opinion of the Investigator.
4. Subject takes prohibited concomitant medications, prescribed or over-the-counter as defined in this protocol.
5. Subject develops an illness that would interfere with his/her continued participation.
6. A prolongation or worsening of overall seizure duration, frequency, type, or pattern considered by the Investigator as serious enough to warrant discontinuation from the study.

7. Subject with an echocardiogram showing a Grade 2 finding (moderate regurgitation/stenosis) if accompanied with moderate to severe signs/symptoms or a Grade 3 finding (severe regurgitation/stenosis) will be discontinued from the study regardless of accompanying clinical symptoms, and should begin discontinuation of the IMP. Additionally, a jump of 2 grades, from Grade 0 to Grade 2 (moderate regurgitation/stenosis) accompanied with moderate to severe symptoms or from Grade 1 to Grade 3 (severe regurgitation/stenosis) will result in subject discontinuation (see [Section 6.3.2](#)).
8. Changes in the ECG that are regarded as clinically significant and/or that worsen over time.
 - An ECG shows an absolute value for QTcB or QTcF ≥ 500 ms or ≥ 60 ms above Baseline.
 - Subject develops second- or third-degree atrioventricular block or another clinically relevant change in ECG as determined by the Investigator.
9. Subject has active suicidal ideation without specific plan as indicated by a positive response (“Yes”) to question 4 of the “Since Last Visit” version of the C-SSRS. The subject should be referred immediately to a mental healthcare professional and may be withdrawn from the study based upon the Investigator’s judgment of benefit/risk of continuing the subject in the study/on IMP.

Subject has active suicidal ideation with a specific plan as indicated by a positive response (“Yes”) to question 5 of the “Since Last Visit” version of the C-SSRS. The subject should be referred immediately to a mental healthcare professional and must be withdrawn from the study.

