11.3.2 Electrocardiograms

The 12-lead ECG recordings will be measured by a qualified technician at the scheduled time points presented in [Table 5-1](#).

All ECG recordings will be performed with the subject resting in the supine position for at least 5 minutes. ECG will be recorded at a speed of 25mm/s and with a calibration of 1cm/mV.

The Investigator should review all ECG recordings and, determine if there are any abnormalities that are considered clinically significant for a particular subject. ECGs will also be sent to a specified central reader for review as detailed in the ECG Manual. The following ECG parameters will be recorded: heart rate, PR-interval, QRS-duration, QT-interval, QTcB or QTcF, and Investigator's conclusion on ECG profile.

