### **3.9 Changes to protocol-defined analyses**

Not applicable; there have not been any changed to protocol defined analyses.

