#### **10.4.2 Electrocardiograms**

ECG parameters include heart rate, PR interval, QRS duration, QT interval, QTcB [QT corrected for heart rate using Bazett's formula], and QTcF [QT corrected for heart rate using Fridericia's formula].

The observed ECG parameter values and their change from Baseline will be summarized (SS) descriptively by treatment group and PSL total group for each scheduled assessment visit. The Last Visit, minimum, and maximum post-baseline values during the Treatment Period will also be included. In addition, the number and percentage of subjects with QTc (Bazett and Fridericia corrected) classifications of <450ms, 450 to <480ms, 480 to <500ms, and  $\geq$ 500ms and change from baseline of <30ms, 30 to <60ms, and  $\geq$ 60ms will be presented for each visit.

For each ECG, the overall ECG result, is also collected, categorized as one of: no abnormality, an abnormal but not clinically significant finding, or a clinically significant finding. The number and percentage of subjects with no abnormality, an abnormal but not clinically significant finding, and a clinically significant finding will be summarized for each of the scheduled assessment visits. Percentages for the visit will be relative to the number of subjects with an ECG result for the visit.

The number and percentages of subjects with abnormal ECG during the Treatment Period will be presented by treatment group and PSL total group. The abnormal ECG criteria are provided in Appendix 13.3. Subject numbers for those meeting abnormal criteria will also be presented.

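### Protocol 13.4.1 promises an arrhythmia summary by arm; SAP 10.4.2 tabulates ECG rate, intervals and an overall result but no arrhythmia type, and SAP 3.9 declares no change

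*Protocol*

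**What the plan says.** Protocol 13.4.1 includes "ECG data (ventricular rate, PR, QTcB, QTcF, and QRS) and arrhythmias" among the safety data that "will be summarized by period, visit, and treatment group". A later sentence of the same section promises a listing of ECG abnormalities, so the listing is additional to the summary and does not replace it.

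Protocol 11.3.2 gives the recorded items as "heart rate, PR-interval, QRS-duration, QT-interval, QTcB or QTcF", followed by the Investigator's conclusion on the ECG. Tracings also go to a central reader under an ECG Manual. Protocol 6.3, criterion 8, gives as a withdrawal ground "Subject develops second- or third-degree atrioventricular block or another clinically relevant change in ECG", listed separately from the QTc limits.

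SAP 10.4.2 states "ECG parameters include heart rate, PR interval, QRS duration, QT interval, QTcB" and QTcF. It plans four outputs:
- observed values and changes by visit;
- QTc categories by visit;
- an overall result by visit at three levels (normal, abnormal without clinical significance, clinically significant);
- counts of subjects meeting the Appendix 13.3 thresholds during the Treatment Period.

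SAP 3.9 says that "there have not been any changed to protocol defined analyses".

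**The concern.** The protocol names arrhythmias in addition to rate and intervals, so tables of rate and intervals do not meet the commitment. A programmer working from SAP 10.4.2 would produce no table by arrhythmia type, and nothing in the SAP would signal that a promised output had been left out.

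The secondary objective is the safety of every dose relative to placebo. Protocol 2.3.1 reports a cardiology review of ectopy and clinically significant arrhythmia across the programme, and plans cardiac monitoring to understand the risk better. Without a summary by type, the final report would have no planned ECG comparison showing whether ectopy or heart block becomes more frequent with dose.

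**Working it through.** No arithmetic applies to the main question; it is a comparison of texts.

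**Step 1. Promise against plan.**

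| ECG output | Protocol 13.4.1 | SAP 10.4.2 and Appendix 13.3 (adults) |
|---|---|---|
| Heart rate | Yes | Values and changes; below 50 or above 120 bpm |
| PR | Yes | Values and changes; treatment-emergent >200, >220, >250 ms |
| QRS | Yes | Values and changes; treatment-emergent >100, >120, >140 ms |
| QTcB, QTcF | Yes | Values, changes, categories, thresholds |
| Arrhythmias | Yes, named separately | None |
| Overall ECG result | Not named | Three levels by visit, nature of the abnormality not given |

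SAP section 10 makes safety summaries by treatment group and padsevonil total, so the covered rows are by arm. In the SAP's current text the word arrhythmia appears only as a sign in the echocardiogram grading table (Appendix 13.4).

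**Step 2. Can interval tables stand in for type?** The protocol itself keeps them apart. Exclusion criterion 13 lists bundle branch block, other conduction abnormalities and irregular rhythms alongside a PR limit. Withdrawal criterion 8 lists AV block apart from QTc. A PR or QRS threshold count describes conduction time; it does not count AV block or ectopy.

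**Step 3. Can adverse event tables stand in?** In part. SAP 10.2 tabulates TEAEs by system organ class and preferred term, and those leading to discontinuation by period. An arrhythmia reported as an adverse event is therefore compared by arm. Whether an ECG finding becomes an adverse event is less certain. Protocol 11.3.1 says that a clinically significant vital-sign abnormality will be recorded as one; 11.3.2 has no matching sentence for ECGs. The definition in 11.1.1.1 is wide enough to include an ECG finding, but it names laboratory and echocardiogram findings and not ECG. The only adverse event of special interest defined in the protocol is potential Hy's Law (11.1.1.2.2), so the SAP's special-interest table does not close the gap.

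**Step 4. How much ECG data is involved?** Table 5-1 schedules post-Baseline ECGs at Visits 3, 4, 5, 7 and 8, which is five. Visit 9 would make six, but it is only for subjects not entering the extension (footnote s), and its ECG is done only if the end-of-treatment or discontinuation ECG was abnormal (footnote i). About 400 subjects are expected to be randomized. The number of planned arm-level tables of arrhythmia by type is zero.

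**Step 5. Is the omission declared?** No. SAP 3.9 records no change.

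**The case against.** The strongest reply is SAP section 1: unless otherwise specified, the study is analyzed as the protocol describes. On that view silence leaves the arrhythmia summary in force, SAP 3.9 is correct, and only detail is missing. This does not settle the matter. The same section says that the SAP defines the scope of the analyses, and 10.4.2 then sets out its ECG outputs item by item. A general clause gives no categories, data source or table to program.

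A second reply is that existing tables already show the important cases. Much of this stands. A reader might infer that the SAP has no conduction summary, or that a subject withdrawn for AV block is visible only in the overall-result row. The documents do not support either reading: PR and QRS are summarized by arm with treatment-emergent thresholds, and an AV block reported as an adverse event would appear in the TEAE tables and, if it caused withdrawal, in the table of TEAEs leading to discontinuation.

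A reader might also infer that rhythm was never recorded. That cannot be decided here. The list in 11.3.2 ends with the Investigator's conclusion, and the content of the central reading is in the ECG Manual. For the same reason, no fixed list of rhythm categories can be assumed to exist in the central data.

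The Data Monitoring Committee's attention to cardiac events (protocol 13.7) neither helps nor hurts: its summaries belong to a separate DMC SAP (SAP 4.3).

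**Conclusion.** The point holds in a narrow form. A safety summary promised in protocol 13.4.1 has no counterpart in SAP 10.4.2 or Appendix 13.3, and SAP 3.9 does not say so. The practical loss is confined to arrhythmias detected on ECG and not reported as adverse events: these would not be compared across arms by type. They would count in the overall-result table only as an abnormality of unstated kind.

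The number of such findings cannot be estimated from the documents. It depends on how consistently Investigators reported ECG findings as adverse events. The efficacy analyses are unaffected. The correction is worth making because the output is already promised and the ECGs are already read centrally. Whether it can be done in full rests on one assumption: that rhythm type was captured, either by the central reader or in the Investigator's conclusion.

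**What to change.** In SAP 10.4.2, add a table of the number and percentage of subjects with treatment-emergent arrhythmia or other rhythm or conduction findings, by type, for each treatment group and padsevonil total, by period and visit as protocol 13.4.1 states. Use the types as actually captured by the central reader or in the Investigator's ECG conclusion, with second- and third-degree AV block identifiable if the data allow. Name the data source in protocol 11.3.2 or in the SAP.

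If rhythm type was not captured, declare and justify the omission in SAP 3.9.

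The cost is one extra table and a line naming its source, provided that the type is held in usable form; otherwise it is one sentence in SAP 3.9.
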